13.3. EVALUATION OF APPLICABILITY OF THE ALGORITHM: DISTRIBUTION OF INTRINSIC CHARACTERISTICS

The distribution of PR/VV delay/AR will be presented by “Eligible” and “not eligible” subjects. An “eligible” subject is one who has at least one complete LV vector test.

The Categories for PR parameters to be considered are :

- i. PR < 120 ms
- ii. $120 \leqslant PR \leqslant 200$
- iii. PR > 200 ms

The Categories for VV delay parameters to be considered are:

- i. VV \leqslant 234 ms
- ii. VV > 234 ms

The Categories for AR parameters are

- i. AR < 170 ms
- ii. $170 \leqslant AR \leqslant 250$ ms
- iii. AR > 250 ms

Chi-square tests will be performed to test if there is an association between eligibility of a subject to the algorithm and the distribution of PR/VVdelay/AR. Two sided p-values will be presented along with a table to present the frequency count of applicability(eligibility) of algorithm (Yes/No) and the distribution of PR/VV delay/AR.

This will be analysed by visit. The analysis will be based on EP.

The population used is EP population

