1. SYNOPSIS

Title:	Clinical evaluation of left ventricular auto threshold algorithm.
Primary objective:	The primary objective of the study is to assess the success rate of left ventricular threshold value identified automatically by “In-Clinic LVAT” feature compared to manual threshold test performed by physician.
Study design:	Multicenter, prospective, non randomized, confirmatory study.
Number of subjects and sites:	59 subjects will be enrolled in approximately 12 sites in Europe.
Study duration:	Approximately 6 months corresponding to 3 months of inclusion period and 3 months of follow-up.
Study population:	Heart failure subjects indicated for cardiac resynchronization therapy (CRT) device implantation according to the current guidelines of the European Society of Cardiology (ESC).
Inclusion criteria:	
Subjects who meet all the following criteria at the time of enrollment may be included:
 
 • Subject already implanted (de-novo, upgrade or replacement) according to the relevant ESC Guidelines [1]: 
 ○ With IS1 Platinium SonR CRT-D (models 1811, 1841, CE marked) for maximum of 5 days, or ○ With IS4 Platinium SonR CRT-D (model 1844, CE marked). • Right atrial, right and left ventricular leads must be implanted. Only bipolar or quadripolar for left ventricle lead. • Reviewed, signed and dated informed consent.
Exclusion criteria:	
Subjects who meet any one of the following criteria at the time of enrollment cannot be included in the investigation:
 
 • Subject included in another clinical study that could confound the results of this study; • Malfunction or dislodgment of right atrial, right and left ventricular implanted leads; • Subject diagnosed with permanent atrial fibrillation; • Known pregnancy; • Minor age; • Under protection or guardianship; • Unavailability for scheduled follow-up or refusal to cooperate.

Device description:	
Platinum SonR CRT-D CE marked:
 
 • DF1/IS1 model 1811 • DF4/IS1 model 1841 • DF4/IS4 model 1844 
Orchestra Plus programming system with 2.54.C1 (or upgraded version) clinical SmartView version.

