2.2. AVAILABLE CLINICAL DATA

2.2.1. *Data from similar features*

a. *Medtronic LVCM*

Left Ventricular Capture Management® (LVCM) algorithm is an automatic feature that monitors the pacing amplitude threshold and adjusts LV outputs. This function helps to ensure delivery of CRT, potentially save time in testing and measuring LV pacing thresholds during subject follow-up.

Therefore, it will automatically balance subject safety and device longevity. LVCM customizes LV pacing outputs to match the needs of individual subjects and analyze LV thresholds over time with trends reports. [10-13]

In the study of Crossley et al. [10], 134 subjects (130 analyzed) from 18 centers, already implanted with a CRT-D system, were enrolled in a clinical trial to evaluate the performance of the LVCM algorithm.

At each follow-up, threshold values were measured manually and with LVCM algorithm. The results were then compared on 307 complete threshold measurement pairs (manual and LVCM in-office tests) collected from 107 subjects for the primary endpoint analysis:

- The difference between LVCM in-office tests and manual threshold tests was within one step in 99.7% (306/307) of the attempts with a two-sided 95% confidence interval of [98.2%, 100.0%].
- LVCM in-office test was identical to the manual LV threshold test in 247 out of 307 attempts (80.72%).

b. *Medtronic VectorExpress*

In the study of Johnson et al. [7], the accuracy of an automated pacing capture thresholds algorithm for quadripolar left ventricular leads called VectorExpress was determined. This algorithm provides automatically the pacing threshold value on all selected LV pacing vectors. Evaluation was performed comparing both threshold values provided by the algorithm and measured manually.

Thresholds were measured for 780 of 992 vectors and at least one vector was measured in 62 of 65 subjects. Results were considered as equivalent if the difference of threshold value provided by manual test and the algorithm was:

- Within $\pm 0.5V$ if manual threshold is strictly inferior to 2.5 V, or
- Within $\pm 1.0V$ if manual threshold is between 2.5 V and 6.0 V.

The accuracy of the automatic algorithm VectorExpress compared to the manual pacing test was 95.3%.

c. *Boston Scientific LVAT (Left Ventricular Auto Threshold)*

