The ELEVATE (Evaluation of LEft Ventricular Auto ThrEshold) study is an acute, prospective, multicenter, pilot study designed to characterize the performance of Boston Scientific LVAT (Left Ventricular Auto Threshold) feature, specifically the commanded mode of LVAT. The study compared the threshold value measured

manually to the one provided by LVAT feature using a surface ECG [14]. The commanded mode of LVAT enables to determine automatically the pacing threshold value of a LV pacing vector.

The LVAT algorithm was able to determine a threshold value in at least one of four LV pacing vectors in 69 of 70 (98.57%) subjects.

The accuracy of the LVAT-determined threshold value was quantified using two different metrics. The threshold determined by the algorithm and by the Corelab matched in 233 of 234 tests (99.5%). In addition, the comparison to the manual threshold value was considered as successful (meaning within two voltage steps) in 96.14% of cases.

Another clinical study sponsored by Boston Scientific is ongoing but not recruiting participants. This clinical trial is called Evaluation of Automatic Threshold Algorithms (CAPTIVATE): see <https://clinicaltrials.gov>. The study aims to evaluate the PaceSafe Right Ventricular Autothreshold (RVAT) and Left Ventricular Autothreshold (LVAT) features for AUTOGEN CRT-D devices. The accuracy of the algorithm will be measured for all subjects, by comparing both threshold values provided by the algorithm and by the Corelab at 1 and 3 months follow-ups. The estimated number of subjects to enroll is 170.

The primary outcomes are:

- The evaluation of the system-related complication-free rate.
- The evaluation of the accuracy of the LVAT Ambulatory test: comparison of threshold value of LVAT algorithm and a Corelab (independent physician). The accuracy of the algorithm will be measured for all subjects, at both 1 and 3 months follow-ups.

The secondary outcome is the evaluation of the percentage of LVAT commanded tests that result in an appropriate outcome. Test outcome would be inappropriate when LVAT threshold could not be determined due to a limitation of LVAT feature and might not occur in manual threshold tests.

The completion date of the study is expected to the end of year 2016.

d. Summary of literature from similar devices

Algorithm	% of subjects with at least 1 test during a follow-up	% of complete* test	% successful** test versus manual test	% successful** test versus ECG

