2.3. SAMPLE SIZE CALCULATION

The study primary objective will be met in case the null hypothesis that the success rate of the “In-Clinic LVAT” is lower than 90% is rejected.

The following assumptions were made to calculate the sample size:

- Power = 80%
- One-sided alpha = 2.5%
- Null Hypothesis proportion of success-rate (target) = 90%

LEVEA – Statistical Analysis Plan

- Expected success-rate = 95%

With these assumptions, it is required to carry out at least 231 LV vector tests. As we will have 5 different pacing vectors for each subject, we will need 47 ($\sim 231/5$) subjects.

An attrition rate of 20% is expected for this study.

Thus the number of subjects needed to be enrolled to obtain 47 evaluable subjects = $47/(1-0.2) = 59$ subjects.

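### SAP 13.3: the chi-square p-values for eligibility against PR, VV and AR are unreliable if only about one to three subjects are non-eligible; exact tests should replace them

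*SAP*

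**What the plan says.** SAP 13.3 splits PR and AR into three categories each and VV delay into two (cut at 234 ms), and cross-tabulates each against eligibility. The test is stated without qualification: "Chi-square tests will be performed to test if there is an association between eligibility of a subject to the algorithm and the distribution of" the three parameters. Two-sided p-values accompany a frequency table, by visit, on the Evaluable Population (EP). There is no minimum expected count and no exact alternative. An eligible subject is one with at least one complete LV vector test.

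Three other places bear on this:

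- SAP 5.7 counts a no-capture or above-5 V result as complete, and SAP 10.4 allows an IS1 subject up to 6 vectors in 3 configurations per visit. A subject therefore has many chances to become eligible.
- Protocol 2.2.1 gives the only subject-level applicability figures, both for other manufacturers' algorithms. For one, "at least one vector was measured in 62 of 65 subjects"; the other found a threshold "in at least one of four LV pacing vectors in 69 of 70 (98.57%) subjects".
- The opening of SAP 13 declares every test in that section hypothesis generating and descriptive. SAP 13.1, in the same section, specifies a Fisher exact test for its own association.

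**The concern.** The Pearson chi-square p-value is a large-sample approximation that needs adequate expected counts in every cell. Here one row of each table, the non-eligible subjects, is likely to hold very few people. The approximation can then make one subject look like strong evidence.

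Protocol 4.1.3 and SAP 10.4 both name a very long inter-ventricular delay as the main reason why the algorithm may not apply. SAP 13.3 is the only planned test of that explanation. If a single non-eligible subject happens to have a VV delay above 234 ms, a small Pearson p-value could be read as confirming the limitation when the data say almost nothing about it.

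**Working it through.** **Inputs from the documents.** Protocol synopsis: "59 subjects will be enrolled in approximately 12 sites in Europe". SAP 2.3: "An attrition rate of 20% is expected for this study", which leaves 47 evaluable. Protocol 2.2.1: non-applicability 3/65 = 4.6% and 1/70 = 1.4%. The size of EP is not stated. It can be at most 59, and I show 47 only as a lower illustration.

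**The plan's own figure.** SAP 2.3 sizes the primary test only. An exact one-sided binomial test of 90% against 95% with 231 tests rejects at 217 or more successes, with alpha 0.0239 and power 0.816. Then 231/5 rounds up to 47, and 47/0.8 rounds up to 59. These figures reproduce. No count of non-eligible subjects is given anywhere, so the rest is conditional.

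**Step 1. Expected non-eligible count, N × (1 − applicability).**

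- N = 59: 59 × 3/65 = 2.7; 59 × 1/70 = 0.8.
- N = 47: 47 × 3/65 = 2.2; 47 × 1/70 = 0.7.

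The probability of none at all runs from (62/65)^59 = 0.06 to (69/70)^47 = 0.51. In that case no association test can be computed.

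**Step 2. Expected cell counts.** With r non-eligible subjects, the expected counts in their row add up to r. If r is 1 to 3, all of them are below 5 whatever the split: at least 2 of 4 cells for VV and 3 of 6 for PR and AR. For all four VV cells to reach 5, r must be at least 10. The binomial probability of 10 or more is below 0.001 at either comparator rate.

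**Step 3. One subject.** Let one non-eligible subject lie in a long-VV group of k out of N. Then

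- Pearson X² = N(N − k) / [(N − 1)k]
- Fisher p = k/N (for k below N/2)

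For N = 59 and an assumed k = 6: X² = 59 × 53 / (58 × 6) = 8.99, p = 0.0027; Fisher p = 6/59 = 0.102. For an assumed k = 12: X² = 59 × 47 / (58 × 12) = 3.98, p = 0.046; Fisher p = 12/59 = 0.203. For a three-category table split 6/35/18 (assumed), with the one subject in the smallest group, Pearson p = 0.011 and the exact p = 0.102.

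**Step 4. True size of the nominal 5% test.** This is the hypergeometric probability, with margins fixed, of all VV tables with p ≤ 0.05. N = 59; every k is an assumption.

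| Non-eligible r | Long-VV k | Smallest expected count | Pearson size | Fisher size |
|---|---|---|---|---|
| 1 | 3 | 0.05 | 5.1% | 0% |
| 1 | 6 | 0.10 | 10.2% | 0% |
| 1 | 12 | 0.20 | 20.3% | 0% |
| 1 | 20 | 0.34 | 0% | 0% |
| 2 | 3 | 0.10 | 10.0% | 0.2% |
| 2 | 6 | 0.20 | 0.9% | 0.9% |
| 2 | 12 | 0.41 | 3.9% | 3.9% |
| 2 | 20 | 0.68 | 11.1% | 0% |
| 3 | 3 | 0.15 | 14.7% | 0.5% |
| 3 | 6 | 0.31 | 2.5% | 2.5% |
| 3 | 12 | 0.61 | 10.2% | 0.7% |
| 3 | 20 | 1.02 | 3.5% | 3.5% |

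Pearson exceeds 5% in seven of the twelve rows and equals Fisher in the other five. In the three-category splits run with 1 to 3 non-eligible subjects, Pearson ranges from 0 to about 10%, and the exact test stays at or below 5%.

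**Step 5. Upper bound.** If the entire 20% attrition (12 of 59) were non-eligible, the Pearson size in the three-category splits run would return to about 4 to 6%. Nothing in the documents supports so many.

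**The case against.** The strongest objection is that little depends on this. SAP 13 labels the tests descriptive, no success criterion uses them, and the frequency table beside each p-value would show a reader that a result rests on one subject. That stands and keeps the point minor. It does not make the p-values that will be printed correct.

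Second, a reader might infer that the chi-square p-values are simply invalid, or always too small. The documents do not support that. They give no distribution of PR, VV or AR, and the size depends sharply on it: in several splits Pearson and Fisher reject exactly the same tables. Unreliable is the right word.

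Third, a reader might take one to three non-eligible subjects as a planned figure. It is not. It is borrowed from other algorithms, and this algorithm's own rate is unknown. The tables are also by visit, and SAP 13.3 does not say how an EP subject with no M1 test is classed, so the M1 count could be higher. The recommendation survives, because an exact test keeps its level at any count.

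Fourth, 47 is not the denominator. In SAP 2.3 it is the number assumed to supply five vector tests each, whereas SAP 13.3 runs on EP. The main figures above therefore use 59.

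Fifth, an exact test is not free of drawbacks. With one non-eligible subject its smallest p-value is k/N, so with k = 6 of 59 it cannot go below 0.10. This also stands.

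**Conclusion.** The concern holds as a minor point about an exploratory analysis. If non-eligibility is about as rare as in the protocol's comparators, every expected count in the non-eligible row is below 5. The Pearson p-value is then unreliable: its true size ranges from 0 to about 20% over the assumed splits, and a single subject can produce p = 0.003 where the exact p-value is 0.10.

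This rests on two assumptions that the documents do not settle: the comparator rates (3/65 and 1/70) and the category splits. A reader might go further and see a threat to the study's conclusion. There is none: the primary endpoint has its own exact binomial test, and applicability itself is reported in SAP 10.4 as counts and percentages with no chi-square test.

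**What to change.** In SAP 13.3:

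1. Replace the chi-square tests with Fisher's exact test for VV delay and the Fisher-Freeman-Halton test for PR and AR.
2. State that no test is done at a visit with no non-eligible subjects.
3. State that the planned frequency table carries the interpretation and that the p-value is secondary to it.
4. Say how a subject with no test at a visit is classed in that visit's table.

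The cost is a few lines of SAP text and a software option. Data collection, sample size and the primary analysis do not change. The one drawback is power: with one to three non-eligible subjects the exact tests will seldom or never reach 0.05. That reflects how little information such a table holds.

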4.1.3. Secondary endpoints

a. Assessment of the diagnostic accuracy of “In-Clinic LVAT” test at M0 follow-up: Independent reviewer validation of LV threshold value provided by algorithm

This endpoint is the number of accurate determination of the pacing threshold value provided by the algorithm feature and an independent reviewer, on all LV pacing vectors and all pacing configurations available at M0 follow-up.

Diagnostic accuracy is defined as an adjudication of LV threshold value provided by the algorithm. The adjudication is based on capture and loss of capture analysis on electrogram strips recorded and stored during “In-Clinic LVAT” tests. The threshold value provided by the algorithm compared to the reviewer adjudication is considered accurate if the difference is within ± 1 step. The reason for incorrect determination of capture/loss of capture (if any) will be reported.

In case several LV Vector Tests were eligible with the same LV pacing vector, in the same pacing configuration, for the same subject, on the same follow-up, only the last one will be considered.

b. Assessment of the success rate of “In-Clinic LVAT” test at M0 follow-up: comparison to manual LV threshold tests results

This endpoint is the success rate of “In-Clinic LVAT” feature on pacing vectors and pacing configurations available at M0 follow-up. The method of analysis is similar to the primary endpoint.

c. Assessment of the success rate of “In-Clinic LVAT” test at M1 follow-up: comparison to manual LV threshold tests results

This endpoint is the success rate of “In-Clinic LVAT” feature on pacing vectors and pacing configurations available at M1 follow-up. The method of analysis is similar to the primary endpoint.

d. Evaluation of the applicability of the algorithm

The algorithm may not be applicable to some subjects, mainly because of a very long inter-ventricular conduction delay. A subject is defined as eligible as soon as one LV Vector Test is complete.

The endpoints for the applicability of the algorithm in the population are:

- The percentage of subjects who are eligible to receive the feature that is the percentage of subjects with at least one complete LV Vector Test at M0 and M1 follow-ups.
- The number of LV Vector Tests attempted, and percentage of completed and successful LV Vector Tests at M0 and M1 follow-ups per subject.

e. Assess the device characteristics in terms of safety and deficiencies

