6.1. TREATMENT AND EVALUATION

6.1.1. *Inclusion follow-up*

Subjects must be informed about the investigation and the potential benefits and risks of the study prior to enrollment. Only those subjects who voluntarily provide written consent to participate will be eligible for enrollment.

The following procedures must be conducted before inclusion of the subject in the study:

- Evaluate subject eligibility based on the inclusion and exclusion criteria
- Obtain written informed consent
- Source data that demonstrate conformance with inclusion criteria should be retained at the investigational site

The following procedures must be conducted in order to include the subject in the study:

- Report implant information
- Report subject's medical history
- Report subject's clinical examination including current vital signs and NYHA classification
- Report subject's current concomitant medications (based on the EDC questions)

6.1.2. *M0 follow-up*

- Perform a complete interrogation of the device with the appropriate clinical programmer
- Print report file
- Measure P-R, A-R and V-V inter ventricular conduction durations on the EGM
- Launch manual LV threshold tests on:
 - 5 common LV vectors to IS1 and IS4 for all subjects,
 - 4 dedicated IS4 LV vectors for subject implanted with IS4 LV lead (LV2-LV4, LV3-LV4, LV3-LV2, LVtip1-LV4).

Manual tests should be performed prior to automatic test to limit bias.

Optional manual threshold tests on additional LV pacing vectors could be performed under physician discretion.

- ECG record:
 - Spontaneous rhythm,
 - Paced rhythm during “In-Clinic LVAT” test in DDD A-test for 30 seconds recording corresponding to 10 seconds before launching test and 20 seconds during the test.
- Launch “In-Clinic LVAT” test on all LV pacing vectors in following pacing configuration:
 - DDD A-test
 - DDD P-test
 - VVI
- Perform right ventricular pacing recordings data collection using RF telemetry to allow collection of multiple EGM:
 - RV A-test

- RV P-test
- Retrieve subject technical data analysis files
- Report Adverse Events and Serious Adverse Events occurred during the testing procedure if any
- Report Device Deficiencies if any

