10.4. EVALUATION OF THE APPLICABILITY OF THE ALGORITHM

The algorithm may not be applicable to some subjects, mainly because of a very long inter-ventricular conduction delay (VV delay). A subject is defined as “eligible” if he/she has at least one complete LV vector test in either of the M0 or M1 visit.

The endpoints for the applicability of the algorithm in the population are:

- A. The number and percentage of subjects who are “eligible” to receive the algorithm. Percentage will be calculated based on the total number of subjects included in the EP, that is:

Number of subjects with at least one complete LV Vector Test at M0 or M1 visits/ Total Number of subjects in EP.

- B. For subject having IS1 lead, up to 6 LV vector tests over 3 LV pacing configurations will be attempted for each subject at each visit.

Among all the subjects having IS1 leads, the number and percentage of subjects having no, one, two,..., six Attempted, Completed and Successful LV vector tests will be presented by LV pacing configuration and visit.

Among all the subjects having IS4 leads, the number and percentage of subjects having one, two,..., fourteen Attempted, Completed and Successful LV vector tests will be presented by LV pacing configuration and visit.

Only subjects with non-missing manual data will be considered.

Percentages calculated based on the number of subjects in EP with the respective lead and configuration will be presented for Attempted, Completed and Successful LV tests.

This information will also be presented with the help of histograms.

This analysis will be based on EP.

This will also be listed.

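### SAP 13.3 relates conduction delay to applicability only through the yes/no 'at least one complete test' outcome, so its exploratory chi-square tests may be uncomputable or weak; completed fraction against delay in ms is a cheap addition

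*SAP*

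**What the plan says.** - **Hypothesis.** Protocol 4.1.3 d states: "The algorithm may not be applicable to some subjects, mainly because of a very long inter-ventricular conduction delay". The next sentence of that section defines a subject as eligible once a single LV vector test is complete.
- **Planned test.** In SAP 13.3 an eligible "subject is one who has at least one complete LV vector test". The section then plans chi-square tests of the "association between eligibility of a subject to the algorithm and the distribution of PR/VVdelay/AR", with the delays categorised. PR is cut at 120 and 200 ms, AR at 170 and 250 ms, and VV once, at 234 ms. On level and population it says: "This will be analysed by visit. The analysis will be based on EP".
- **Data available.** For IS1 subjects, SAP 10.4 B says "up to 6 LV vector tests over 3 LV pacing configurations will be attempted for each subject at each visit". SAP 5.6 lists 14 vectors and three configurations for IS4. The delays are recorded as durations: "Measure P-R, A-R and V-V inter ventricular conduction durations on the EGM" (protocol 6.1.2, repeated for M1 in 6.1.3).
- **Related analysis.** SAP 10.4 B tabulates, plots and lists the number of completed tests per subject, but not by delay, and only for subjects with manual data.
- **Status.** The opening of SAP section 13 labels any test there as hypothesis generating and descriptive. No power or significance level is attached to 13.3.

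**The concern.** The protocol names one expected limit of the algorithm, and SAP 13.3 is the only place where it is examined. A subject with 1 of 18 tests complete is coded the same as one with 18 of 18. If almost every subject has at least one complete test, the outcome hardly varies. The p-value is then either uncomputable or unlikely to detect a gradual effect of delay. A non-significant result could be taken as evidence that delay does not matter, although per-test completion, where most of the variation may lie, is already collected. The primary endpoint is not affected.

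**Working it through.** **1. The plan's own figures.** SAP 13.3 states no sample size. The only one in the documents is for the primary endpoint (SAP 2.3), and it reproduces. An exact one-sided binomial test with n = 231 and success at 217 or more has alpha 0.0239 and power 81.6%. Then 231/5 = 46.2, so 47 subjects, and 47/(1 − 0.2) = 58.75, so 59. The evaluable population is therefore taken as N = 47 to 59.

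**2. Tests per subject per visit.** IS1: 6 × 3 = 18. IS4: 14 × 3 = 42.

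**3. How rare non-eligibility may be.** Protocol 2.2.1 reports at least one measured vector in 62 of 65 subjects for one similar algorithm and in 69 of 70 for another. The non-eligible rates q are 3/65 = 4.6% and 1/70 = 1.4%. The summary table there gives 78% and 89% of tests complete, so 22% and 11% of tests were not complete. Expected non-eligible subjects are N × q, and the chance of none is (1 − q)^N.

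| N | q | Expected | Chance of none |
|---|---|---|---|
| 47 | 1.4% | 0.7 | 51% |
| 59 | 1.4% | 0.8 | 43% |
| 47 | 4.6% | 2.2 | 11% |
| 59 | 4.6% | 2.7 | 6% |

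With none, no test can be computed. The smallest expected cell is N × q × (share with VV above 234 ms). That share is not in the documents. For shares of 10% to 50% the cell runs from 47 × 0.014 × 0.1 = 0.07 to 59 × 0.046 × 0.5 = 1.4, so the chi-square approximation is unreliable even when the test exists.

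**4. Power against a graded effect.** Assumptions: logistic-normal completion; 18 tests per subject; two-sided 5%; correlation 0.4 between VV and the subject's propensity to complete; 10%, 25% or 50% of subjects above 234 ms. The model was solved to give 78% completion with 4.6% of subjects at zero (intercept 3.20, SD 3.75), or 89% with 1.4% (intercept 4.98, SD 3.64).

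| N | Chi-square as planned | Fisher, same table | Spearman, completed fraction on VV in ms |
|---|---|---|---|
| 59 | 0.3% to 29% | 0% to 14% | 65% to 78% |
| 47 | up to 29% | 0% to 9% | 54% to 68% |

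Spearman type I error was 3% to 6%. The 1.4% figure was observed on four vectors per subject. Calibrating to four vectors instead (SD 1.94) puts the chance of 0 of 18 at 0.13%. Chi-square power is then 1% to 4% and Spearman 67% to 68%, and over 90% of simulated trials have no non-eligible subject.

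**5. Which reduction costs more.** A second simulation used N = 47 and 59, half IS1 and half IS4, 20% of subjects above the VV cut, completion 78% or 89%, and between-subject SD 2 or 4 logits:

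| Outcome / VV | Slope 1 logit per SD | Slope 2 |
|---|---|---|
| Yes/no, VV category (Fisher) | 0% to 7% | 1% to 18% |
| Yes/no, VV in ms | 2% to 11% | 9% to 32% |
| Fraction, VV category | 17% to 60% | 48% to 97% |
| Fraction, VV in ms | 23% to 87% | 68% to 100% |

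Changing the outcome recovers most of the power; dropping the VV cut adds less.

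**6. Where the result weakens.**
- *Confined effect.* If every non-eligible subject has VV above 234 ms, q = 4.6% and only 10% to 20% of subjects have long VV, Fisher power on the planned table is 56% to 79%.
- *Commoner non-eligibility.* At an assumed 10% non-eligible and 20% with long VV, Fisher power with 59 subjects is 48% (risk ratio 5) or 77% (risk ratio 10).
- *Pure step at the cut, 10% or 25% of subjects above it.* For a large step, chi-square gives 23% to 57% and a Wilcoxon comparison of the fraction 66% to 95%. For a small step the figures are 10% to 21% and 21% to 36%, with one case a tie.
- *Near-complete testing.* Protocol 2.2.2 reports one test without a threshold among 115 + 204 = 319 recordings, so 318/319 = 99.7% complete. At 99.7% (59 subjects, 18 tests, correlation 0.3 to 0.4, SD 1 to 3.7) Spearman power is only 4% to 12%. It is 17% to 43% at 98% completion and 28% to 56% at 95%. Chi-square stays at 0% to 4%.

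**The case against.** The strongest reply is that one-test eligibility is the protocol's definition, not an SAP invention. Applicability is posed per subject, and the completed fraction answers a neighbouring question. That stands. A reader might infer that the dichotomy is an error and that the eligibility analysis should be replaced; the documents do not support this, and the eligibility tables should stay.

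Second, the analysis is labelled exploratory, no power is promised, and the per-subject completion counts will be listed, so later exploration remains possible. That also stands and limits the importance of the point. It does not make an uninformative p-value useful.

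Third, a reader might infer that the tests are almost bound to be non-significant. That goes too far. The completion rates come from other manufacturers' algorithms, and this algorithm's rate, the VV distribution and the effect size are not in the documents. The protocol's reference to very long delay also makes a threshold effect plausible, which favours the planned table. The basis for 234 ms may lie in the Investigator's Brochure, which is not available here, so the cut cannot be called arbitrary.

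Finally, SAP 5.7 is ambiguous about attempted tests. Its text requires that a test was neither interrupted nor aborted, while Table 3 counts such tests as attempted. On the text's reading the completed fraction would be close to 1 for everyone, so any remedy must fix the denominator.

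**Conclusion.** The point holds as a low-cost improvement to an exploratory analysis. At the comparator rates about 1 to 3 of 47 to 59 subjects would be non-eligible, and possibly none. The planned chi-square tests would then often be uncomputable, or have roughly 0% to 29% power against a graded VV effect at correlation 0.4, against about 54% to 78% for the completed fraction on VV in ms. SAP 5.7 counts a no-capture or above-5 V result as complete, which makes non-eligibility rarer still. Most of the loss comes from the yes/no outcome.

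This rests on borrowed completion rates and an assumed VV distribution and effect size. The benefit shrinks if completion is near 99.7%, and it narrows or reverses if non-eligibility is confined to a small long-VV group. PR and AR were not simulated, so no power figure is claimed for them.

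**What to change.** In SAP 13.3:

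1. Keep the eligible/not-eligible by category tables as description, without chi-square p-values.
2. Add, by visit on the evaluable population, each subject's completed fraction: completed tests divided by all launched tests. Count aborted, interrupted and no-value tests as attempted, in line with SAP Table 3. Do not require a manual value.
3. Relate this fraction to PR, VV and AR in ms by Spearman correlation with 95% CI, one value per subject, with a scatter plot to show any non-monotone relation.
4. Compare the fraction between VV ≤ 234 and > 234 ms by the Wilcoxon rank-sum test, which covers a step effect that Spearman may miss.
5. Report overall and by pacing configuration and lead type, labelled hypothesis generating.

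The cost is SAP wording and a few lines of code. Completions are already in the Real-Time Data files and the delays are measured at M0 and M1. The downside is some extra exploratory output, on a question related to the protocol's yes/no eligibility but not identical to it.
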